Protocol: Evaluation of oral condition and the effect of dental treatment on physical parameters of athletes

Researcher: [name]

Approval of the Research Ethics Committee in Brazil: 93416718.1.0000.0081

Approval date: 09/August/2018

Main goal

Evaluate the oral condition and propose dental treatment according to the needs of athletes linked to the Faculty of Physical Education of the Santo Amaro University.

Secondary objectives.

- Comparing the athlete's performance through physical tests of strength, speed, endurance, before and after dental treatment;
- Relate the oral conditions found with the specific habits of each sport;
- Assess the effect of biofilm control on the oral and performance conditions of the evaluated athletes.

Protocol:

This research project will comply with Resolution No. 196, of October 16, 1996, of the National Health Council, and the Dental Professional Code of Ethics (Resolution CFO No. 042/2003).

All recruited individuals will be offered verbal and written explanations of the objectives, methodology, benefits and possible risks related to participation in the project. Thus, individuals who accept to participate in the study, will sign the Free and Informed Consent Term, previously evaluated and approved by the Research Ethics Committee involving human beings of UNISA.

3.1-Experimental design

Students and / or athletes linked to the Faculty of Physical Education of the University Santo Amaro must be evaluated. According to an initial survey, about 120 individuals should be examined. Clinical parameters such as decayed, lost and / or filled dental index (CPO) and periodontal parameters such as probing depth (PS), clinical level of insertion (NCI), plaque index (IP) and bleeding index (IS) will be evaluated . Physical tests of strength, speed and resistance should be performed and periodontal therapy should be performed according to the needs presented by each individual. After 90 days, new clinical examinations and physical tests should be performed.

3.2-Selection of patients

Individuals practicing physical activities linked to UNISA will be included. Initially, we will have a convenience sample that will later be stratified into groups for evaluation and analysis. Individuals with systemic pathologies, smokers, should be included in the study

Patients with any of these characteristics should be excluded from the study: pregnancy or lactation, use of antibiotics in the last 3 months, phenytoin, calcium antagonists, cyclosporine or anti-inflammatory drugs one month before the initial consultation, use of oral or replacement contraceptives hormonal, periodontal treatment in the 6 months prior to the start of the study.

After being properly informed about the nature of the study, individuals must sign a free and informed consent form.

Patients will be submitted to periodontal treatment in undergraduate and graduate clinics at the UNISA Department of Dentistry, according to the needs presented.

3.3-Clinical evaluation

Patients will be evaluated by a previously trained and calibrated periodontist. Of the sample, 10% will be examined twice for each of the clinical criteria evaluated, in order to obtain the inter-examiner diagnostic reliability measured by Kappa statistics (between 0.8 and 1.0) and intra-examiner using the standard error of the measurement. (EPM). In the periodontal clinical examination, measurements will be obtained for probing depth and clinical level of insertion performed at six points per tooth: mesio buccal, labial mesio, buccal mesio, mesio lingual / palatine, lingual / palatine medium, this lingual / palatine, using periodontal probe manual (PCPUNC 15, Hu-Friedy, Chicago, USA). For Plaque Index and Gingival Index (Ainamo & Bay, 1975), dichotomous evaluation will be performed on the faces: vestibular, mesial, distal and lingual / palatal.

Patients will be observed in two stages, as shown in figure 1, prior to the start of treatment (T0) where clinical examinations will be performed, radiographs will receive dental scaling and root planing treatment (T1) and 90 days after therapy (T2) will be evaluated again (Nakamura-Minami, et al., 2003; Figueredo et al., 2004; Gomi, et al., 2007).

3.4- Physical Evaluation

The following demographic variables will be assessed: age, sex, race and education. We will adopt the following inclusion criteria: Be a practitioner of one of the modalities investigated for more than 5 years and perform more physical activity than the minimum recommendations per week, for this analysis we will use the international physical activity questionnaire.

The evaluations performed will be: Aerobic running performance evaluation test, critical speed in swimming, body composition evaluation, muscle strength through the 1RM test in the bench press and short-term heart rate variability at rest. The evaluations proposed by the present study will be carried out in three days, with an interval of 24 hours.

Risk stratification for cardiovascular events during exercise will be performed according to the ACS recommendations. An anamnesis will be performed based on the following cardiovascular risk factors: age, family history of cardiovascular disease, smoking, high blood pressure, dyslipidemia or hypercholesterolemia, diabetes or hyperglycemia.

3.5- Periodontal Therapy

Periodontal treatment will start after physical tests of strength, speed and endurance. The individuals evaluated in this study will receive instructions on oral hygiene, including brushing technique and use of dental floss / tape, and treatment of dental scaling and root planing (RDAR).

After anamnesis, the individuals included will receive instructions for individualized oral hygiene. The treatment of RDAR will be performed in a single session (full-mouth disinfection) according to the established protocol (Quirynen et al 1999, 2006), with two sessions carried out in 24 hours.

The individuals will be treated by a single periodontist and the scraping and planing procedures will be performed on all teeth as follows: local anesthetic infiltrative type of the areas to be treated, RDAR using Gracey 5/6 carbon steel curettes, 11/12, 13/14 and MacCall 13/14, 17/18 curettes, according to their therapeutic indications. Polishing the quadrants treated with abrasive paste; oral hygiene instructions including brushing of the Bass type, dental floss and sometimes toothbrush inter dental or unitufo (Apatzidou; Riggio, Kinane, 2004, Jervoe-Stormet al., 2006).

After the dental scaling and root planing procedures, 90 days should be waited for reassessment and conducting the new clinical and physical exams. The individuals will then be referred to the clinics in operation at the Faculty of Dentistry of UNISA according to their needs.

3.6 - Statistical analysis

Analysis of variance (ANOVA) will be used to compare the averages of dental clinical values and physical tests. Parametric and non-parametric values should be analyzed. The analyzes and graphs of the present study will be performed with the aid of the statistical program graphPad Prism version 4.0. The data present in the graphs will be expressed as mean \pm SEM (standard error of the mean).

With the objective of studying the association between the probing depth, presence of plaque, presence of bleeding and existence of maintenance variables, as the physical exercises performed before and after dental treatment generalized estimating equation models should be used. The score test will be used to test the target hypotheses, because the observations are dependent. The Gaussian with an identity link function will be applied. The half-normal probability plot with a simulated envelope¹⁵ made it possible to observe that the model was well adjusted. R software, version 3.2.5, will be used to analyze the data and a significance level of 5% was considered for all the tests.

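### The title and the performance part of the third secondary objective claim an effect, but one test before therapy and one at 90 days with no described comparison group can show only change

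*Combined protocol and SAP*

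**What the plan says.** The title announces "the effect of dental treatment on physical parameters of athletes". The third secondary objective is to "Assess the effect of biofilm control on the oral and performance conditions of the evaluated athletes". The first secondary objective is worded more modestly, as a comparison of performance before and after treatment, and the main goal concerns oral condition and treatment need.

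On timing, section 3.5 states: "Periodontal treatment will start after physical tests of strength, speed and endurance". Sections 3.1 and 3.5 place the second round of physical tests 90 days later. Section 3.3 speaks of two observation stages. The three test days in section 3.4 make up one battery, not a repeated baseline.

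On who is treated, section 3.5 says: "The individuals evaluated in this study will receive instructions on oral hygiene", and goes on to scaling and root planing. Sections 3.1 and 3.2 tie therapy to need: "periodontal therapy should be performed according to the needs presented by each individual" and "Patients will be submitted to periodontal treatment in undergraduate and graduate clinics at the UNISA Department of Dentistry, according to the needs presented". Section 3.2 also says that "we will have a convenience sample that will later be stratified into groups for evaluation and analysis", but does not define the groups or say that any of them is untreated.

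On analysis, section 3.6 names ANOVA for dental and physical means. It also names a Gaussian GEE with identity link and a score test, for the association of probing depth, plaque, bleeding and maintenance with the physical tests before and after treatment. It lists no comparison contrast and no covariate for training or season. Activity is measured by questionnaire, but for the inclusion criterion ("for this analysis we will use the international physical activity questionnaire", section 3.4).

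**The concern.** An effect of treatment is the difference between what happened and what would have happened without treatment. With one measurement on each side of therapy, the second quantity is never observed. The athletes go on training for 90 days, the season moves on, and they meet the tests a second time. Any shared change from these sources enters the before/after difference in full.

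At stake is the headline claim. A significant rise could be reported as a benefit of dental treatment when treatment did nothing for performance. A shared decline, for example out of season, could hide a real benefit. A similar problem reaches the GEE if it has no term for visit: plaque falls after therapy, so a shared gain at T2 would also look like an association between lower plaque and better performance.

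**Working it through.** The plan gives no power, SD, expected change or derived sample size, so there is no figure of its own to reproduce.

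**Inputs from the documents.** About 120 individuals (section 3.1); two test occasions, before therapy and at 90 days (sections 3.1 and 3.5); 5% significance level (section 3.6).

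**Assumed inputs.** Two-sided test; ANOVA taken as a repeated-measures comparison of two visits, which equals a paired t-test; true treatment effect zero; shared gain g of 0.05 or 0.10 SD of the test score; T0–T2 correlation ρ of 0.8, 0.9 or 0.95; n = 60 as a second case, because the number of completers is not given.

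**Before/after comparison.** The expected difference is treatment effect + shared change. With zero effect it equals g. The SD of individual change is √(2(1−ρ)), so the standardised change is dz = g/√(2(1−ρ)), and the non-centrality is dz·√n.

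For g = 0.10:
- ρ = 0.8: 0.10/√0.4 = 0.158; × √120 = 1.73
- ρ = 0.9: 0.10/√0.2 = 0.224; × √120 = 2.45
- ρ = 0.95: 0.10/√0.1 = 0.316; × √120 = 3.46

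The upper-tail rejection probability from the non-central t distribution is the share of studies that show improvement:

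| Shared gain | n | ρ = 0.8 | ρ = 0.9 | ρ = 0.95 |
|---|---|---|---|---|
| 0.05 SD | 120 | 14% | 23% | 40% |
| 0.10 SD | 120 | 40% | 68% | 93% |
| 0.05 SD | 60 | 9% | 13% | 23% |
| 0.10 SD | 60 | 23% | 40% | 67% |

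With no shared change the upper tail would be 2.5%. A shared loss of the same size gives the same percentages for apparent deterioration.

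**GEE, only if it has no visit term.** Simulation with 2,500 runs, exchangeable working correlation, zero effect, g = 0.10. Further assumptions: plaque falls by 1 SD, has T0–T2 correlation 0.5, and is independent of fitness. The score test finds a false association of lower plaque with better performance in 19%, 36% and 64% of studies at n = 120, and in 12%, 21% and 36% at n = 60 (ρ in the same order). With g = 0 it rejects in 4% to 5%.

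**GEE with a visit term.** If plaque is independent of stable fitness, the plaque term rejects in 5% to 6% at n = 120 (robust Wald test), so the visit term is sufficient. If plaque at T0 has an assumed correlation of −0.3 with fitness, the plaque term rejects in 14% to 53% when plaque at both visits is tied to fitness, and in 10% to 34% when only T0 plaque is. It then also picks up stable differences between athletes. In those same settings, a GEE with visit, athlete-mean plaque and within-athlete deviation rejects in about 5% to 8% (robust Wald test), and a regression of change on change in 4.5% to 5.8%. With two visits and complete data, the within-athlete slope from the split model equals the slope from the change-on-change regression.

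**The case against.** The strongest reply is that the claim is narrow. The main goal is about oral condition, the first secondary objective only compares before with after, no primary performance endpoint is named, and nothing says that a significant change will be read causally. This stands, and it limits the severity. It does not rescue the title or the third objective, both of which speak of an effect.

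Secondly, section 3.6 already presents the GEE as a study of association, and its mention of before and after treatment may be meant as the visit factor. This also stands. A reader might infer that the plan leaves time out of the model. The documents do not support that: the sentence is unclear, and no visit term is named but none is excluded. The GEE figures without a visit term are therefore conditional.

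Thirdly, athletes with more than five years' practice and above-minimum activity may have little left to gain from training. That may be so, but it does not establish familiarity with every test or rule out seasonal change.

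Fourthly, Figure 1 was not available in the text reviewed, the sample is to be stratified, and need-based therapy might leave some athletes untreated. The text around the figure describes two stages and no second group. The strata are undefined, and athletes left untreated for lack of need would differ from the treated at baseline. None of this supplies the missing comparison.

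Finally, a reader might infer that a visit term is inadequate and the GEE must be replaced. That goes too far. The visit term falls short only if oral status is correlated with stable fitness, and a split oral covariate then deals with it inside the GEE.

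**Conclusion.** The point holds for the title and for the performance part of the third secondary objective. As described, the design measures change after therapy and cannot separate treatment from shared retest, training or seasonal change. This follows from the design and needs no assumed figure. The percentages do rest on assumptions: under a shared gain of 0.10 SD and correlations of 0.8 to 0.95, false improvement appears in 40% to 93% of studies at n = 120 and in 23% to 67% at n = 60. The real size and direction of any shared change cannot be known from the documents.

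A reader might infer that the whole study is invalid. The documents do not support that, because the main goal is untouched, as is the first secondary objective read as a description of change. This is a should-fix: the headline wording is stronger than the design, and the remedy is cheap.

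**What to change.** 1. Restate the title and conclusions as *change in physical parameters after periodontal therapy*. Restate the performance part of the third objective as *association of change in plaque and bleeding with change in performance*.
2. State in section 3.6 that the before/after comparison is descriptive and will not be interpreted causally.
3. State that the GEE includes a visit term, and split each oral measure into athlete mean and within-athlete deviation. Equivalently, regress the T0–T2 change in each physical test on the T0–T2 change in one oral measure named in advance, with an intercept that absorbs the shared change. The split matters if oral status is correlated with stable fitness, which is an assumption.
4. Optionally, repeat the activity questionnaire at T2 and add its change as a sensitivity covariate.

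**Cost.** Wording and a clearer model statement, using data already planned for T0 and T2. No new athletes or visits are needed.

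**Downside.** The claim is more modest and power is limited. For an assumed true extra gain of 0.10 SD per SD of plaque reduction, the change-on-change slope is significant in 40%, 67% and 93% of studies at n = 120 (ρ = 0.8, 0.9, 0.95), and in 22%, 39% and 66% at n = 60. If the measured plaque change has reliability 0.7, these fall to 30%, 52% and 80%, and to 17%, 29% and 50%. The association also stays confounded if training gains differ between athletes whose oral status changes more or less.

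Separately, the passages that tie therapy to need (sections 3.1 and 3.2) and the description of scaling on every tooth (section 3.5) should be reconciled. That is a point of its own.

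### The text does not settle who is scaled or to what extent, and without a control group the T0–T2 change cannot carry the effect wording of the title and secondary objective 3

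*Combined protocol and SAP*

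**What the plan says.** **Treatment according to need.** Section 3.1 says that "periodontal therapy should be performed according to the needs presented by each individual". Section 3.2 says: "Patients will be submitted to periodontal treatment in undergraduate and graduate clinics at the UNISA Department of Dentistry, according to the needs presented". Neither section defines need.

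**Treatment of everyone evaluated.** Section 3.5 says: "The individuals evaluated in this study will receive instructions on oral hygiene". The same sentence goes on to scaling and root planing for the same people. It then says "The individuals will be treated by a single periodontist" and "the scraping and planing procedures will be performed on all teeth as follows". Section 3.3, in a sentence whose grammar is damaged, says that patients "will receive dental scaling and root planing treatment (T1) and 90 days after therapy (T2) will be evaluated again". Neither section attaches a need condition.

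**Entry.** Sections 3.2 and 3.4 select on university affiliation, years of practice and activity level. Section 3.2 excludes for pregnancy or lactation, certain medicines, and recent periodontal treatment. No criterion requires periodontal disease.

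**Comparison.** The athletes are examined and tested before treatment and again at 90 days. Section 3.2 mentions later stratification of a convenience sample into groups but does not define them. No untreated or delayed-treatment group is described. Under 3.5, referral for other dental needs follows the 90-day examinations.

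**Claims.** The title names an effect of dental treatment on physical parameters. Secondary objective 3 names an effect of biofilm control on oral and performance conditions. Secondary objective 1 and the generalized estimating equation (GEE) paragraph in 3.6 use before/after wording, and 3.6 speaks of association.

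**The concern.** There are two linked problems.

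First, the intervention behind the T0–T2 change depends on which section is followed. Under 3.5 every athlete evaluated is scaled. Under 3.1 an athlete judged to have no need might not be. That athlete would have no therapy date, yet 3.3 and 3.5 count the 90 days to T2 from therapy. Section 3.1 re-tests after 90 days without limiting this to treated athletes, and 3.6 names no variable for treated status. A reader of the results could not tell which population the mean change describes.

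Second, on either reading the change also contains whatever else happens over 90 days: training, season, and familiarity with the tests. With no concurrent comparison these cannot be separated from treatment. The treatment before T2 is also a periodontal package only, which is narrower than dental treatment as the title uses the term. A significant change in strength, speed or endurance, reported under the present title, would be read as a causal result about dental care.

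**Working it through.** **Step 1: the sections side by side.**

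| Question | 3.1 and 3.2 | 3.3 and 3.5 |
|---|---|---|
| Who is treated | Those with need; need undefined | The individuals evaluated; no condition |
| Extent | According to need (3.1) | All teeth (3.5) |
| Where, by whom | Undergraduate and graduate clinics (3.2) | A single periodontist (3.5) |
| Start of the 90 days | Not tied to treated status (3.1) | From therapy |

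Section 3.5 also contains "local anesthetic infiltrative type of the areas to be treated" and a similar phrase about the quadrants treated. Either could mean that need governs extent. The text does not choose between these readings.

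**Step 2: what is given before T2.** Section 3.5 lists hygiene instruction, scaling/root planing and polishing. Referral for other needs comes after T2. The comparison therefore concerns this package only.

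**Step 3: how far a non-treatment shift alone could go.** The plan gives no effect size, standard deviation, power or dropout, so it has no figure of its own to reproduce. This step is an illustration.

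Inputs from the documents:
- about 120 individuals to be examined (3.1);
- a 5% significance level (3.6).

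Assumptions:
- a two-sided test, since sidedness is not stated;
- a paired t-test as a stand-in for the planned before/after analysis;
- no treatment effect;
- a shift d from training or repeat testing of 0.10, 0.20 or 0.26 SD of the change scores;
- n = 120, 90 or 60 athletes re-tested, because 120 is the number examined, before exclusions and dropout.

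The largest shift, 0.26, is about the change that 120 pairs detect with 80% power: (1.960 + 0.842)/√120 = 0.256.

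The smallest observed mean change that reaches p < 0.05 is t(0.975, n−1)/√n:
- n = 120: 1.980/10.954 = 0.181 SD
- n = 90: 1.987/9.487 = 0.209 SD
- n = 60: 2.001/7.746 = 0.258 SD

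The probability of a significant result comes from the noncentral t distribution with n−1 degrees of freedom and noncentrality d√n. For n = 120 the noncentralities are 1.095, 2.191 and 2.848.

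| Re-tested | d = 0 | d = 0.10 | d = 0.20 | d = 0.26 |
|---|---|---|---|---|
| 120 | 5% | 19% | 58% | 81% |
| 90 | 5% | 16% | 47% | 68% |
| 60 | 5% | 12% | 33% | 51% |

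At n = 120 the unrounded values are 0.192, 0.584 and 0.807. A simulation of 40,000 trials gave 0.194, 0.587 and 0.807.

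**The case against.** The strongest defence is that 3.5 is the operative therapy section and 3.1 only a summary. Need in 3.1 may mean the extent of therapy, with 3.5 supplying the detail. Section 3.2 may describe the later referral, since it names teaching clinics where 3.5 names one periodontist. Section 3.3 refers to figure 1, which is not available in this text and may show who proceeds to T1. The supporting sentence in 3.3 is garbled and is weak evidence by itself.

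Much of this stands, and it limits the point to saying that the available text does not settle the question. It does not remove the difference in wording: 3.2 says periodontal treatment, and 3.5 covers the individuals evaluated and all their teeth.

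It is also fair to say that a before/after description is a legitimate aim. Objective 1 and 3.6 make no effect claim; only the breadth of the term dental treatment is open there. The undefined groups in 3.2 bear on mixed populations, but they do not supply a control.

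A reader might infer two stronger things that the documents do not support:
- **That a known share of athletes goes unscaled and dilutes the mean by a calculable amount.** No share is given, and no passage describes athletes who receive hygiene instruction alone.
- **That 81% is this trial's false-positive rate.** It is the upper end of an illustration that assumes the largest shift and the return of all 120 athletes.

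**Conclusion.** The point holds in a limited form. Sections 3.1 and 3.2 differ from 3.3 and 3.5 on who is treated and to what extent, and no entry criterion closes the gap. The population behind the T0–T2 change is therefore undefined in the available text; figure 1 might narrow this but would not remove the conflict in wording. That part rests on the text alone.

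The effect wording in the title, and in secondary objective 3 as regards performance, claims more than an uncontrolled before/after comparison of a periodontal package can show. This follows from the design and needs no numerical assumption. The calculation only indicates scale: assumed non-treatment shifts of 0.10 to 0.26 SD of the change would give a significant result in 12 to 51% of trials with 60 athletes re-tested, and in 19 to 81% with 120. The documents give neither the size of any shift nor the number expected to return.

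The before/after comparison itself need not be abandoned. What should change is what is claimed from it.

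**What to change.** 1. The sponsor must reconcile 3.1 and 3.2 with 3.3 and 3.5 on who is treated and to what extent. This review does not say which is right.
2. Restate the title and secondary objective 3 as the before/after change accompanying the periodontal package of hygiene instruction, scaling/root planing and polishing. In secondary objective 1 and the GEE text of 3.6, only replace the term dental treatment with that package.
3. State that, without a control group, this change cannot be separated from time, training or repeat testing.
4. If the reconciled text leaves some athletes unscaled:
   - record treated status and the criterion used;
   - state the date from which their T2 is counted;
   - keep all re-tested athletes in the main before/after comparison;
   - report change by treated status descriptively only, with a caution about confounding by baseline disease and regression to the mean.

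The cost is protocol wording and, only in the case under item 4, one extra data field. No visits or athletes are added. The downside is a narrower claim and, if results by treated status are reported, smaller groups that support description only.

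### Smokers and people with systemic disease are eligible, but section 3.6 does not pre-specify adjustment for either, so the between-person oral-performance association may be confounded

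*Combined protocol and SAP*

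**What the plan says.** **Eligibility (section 3.2).** The plan states "Individuals with systemic pathologies, smokers, should be included in the study". The exclusion list that follows names neither smoking nor systemic disease. It does remove people by medication: "use of antibiotics in the last 3 months, phenytoin, calcium antagonists, cyclosporine or anti-inflammatory drugs one month before the initial consultation", and also "use of oral or replacement contraceptives hormonal".

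**Stratification (section 3.2).** "Initially, we will have a convenience sample that will later be stratified into groups for evaluation and analysis". The stratifying factors are not given, and section 3.6 does not return to these groups.

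**Data collected (section 3.4).** The history taken to stratify cardiovascular risk during exercise covers age, family history and "smoking, high blood pressure, dyslipidemia or hypercholesterolemia, diabetes or hyperglycemia". Its stated use is exercise safety, and no link to the analysis is made.

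**Analysis (section 3.6).** ANOVA compares mean dental and physical values. For the association, the text begins "With the objective of studying the association between the probing depth, presence of plaque, presence of bleeding and existence of maintenance variables", relates these to the physical tests before and after treatment, and says that "generalized estimating equation models should be used". The model is Gaussian with an identity link and uses score tests at the 5% level. No covariate or stratum for smoking or systemic disease is named. The remark there that the model was well adjusted refers to a half-normal plot, which checks fit and is not covariate adjustment.

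**The concern.** Smoking and chronic disease can plausibly affect both the periodontal measurements and physical performance. If they do so in this sample, athletes with deeper pockets or more bleeding would tend to perform worse even if oral condition had no effect on performance.

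A GEE fitted to two visits per athlete, with the oral measures as explanatory variables, uses differences between athletes as well as changes within them. The between-athlete part carries the effect of any omitted common cause. The result could be reported as a link between oral health and performance when some or all of it reflects who smokes or is ill. Leaving adjustment unspecified also allows the choice to be made after the results are seen.

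**Working it through.** The plan gives no figure to reproduce. The target of about 120 comes from an initial survey, without an effect size, SD or power. The documents give neither the prevalence of smoking or disease nor their effects, so what follows is an illustration under stated assumptions.

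**Inputs.** From the documents: n = 120 and a 5% level (taken as two-sided, since this is not stated). Assumed: a yes/no factor with prevalence p that shifts the oral measure by a SD and performance by b SD, with no true association otherwise.

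**Step 1: induced correlation, in absolute value.**

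r = p(1−p)ab / √[(1 + p(1−p)a²)(1 + p(1−p)b²)]

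**Step 2: chance that a 5% test of no association rejects.**

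f = atanh(r) × √(n−3), with √117 = 10.82; rejection = Φ(f − 1.96) + Φ(−f − 1.96)

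*Low end:* p = 0.10, a = 0.5, b = 0.4. p(1−p) = 0.09; r = 0.018 / √(1.0225 × 1.0144) = 0.018; f = 0.19; rejection about 5.4%.

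*High end:* p = 0.30, a = 1.0, b = 0.8. p(1−p) = 0.21; r = 0.168 / √(1.21 × 1.1344) = 0.143; f = 1.56; rejection about 34.5%.

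With equal shifts (a = b = d):

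| p | d | r | rejection |
|---|---|---|---|
| 0.05 | 0.3 | 0.004 | 5.0% |
| 0.10 | 0.5 | 0.022 | 5.7% |
| 0.20 | 0.5 | 0.038 | 7.0% |
| 0.30 | 0.5 | 0.050 | 8.4% |
| 0.30 | 0.8 | 0.118 | 25.1% |

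**Step 3: closer to the planned model.** Steps 1 and 2 use a single-visit correlation. A simulation of a two-visit Gaussian GEE (exchangeable correlation, visit term, Wald test, no true association, 400 runs per row) gave these rejection rates:

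| p | d | GEE without the factor | GEE with the factor | before-after change |
|---|---|---|---|---|
| 0.10 | 0.5 | 7.25% | 6.75% | 5.25% |
| 0.10 | 0.8 | 11% | 6.5% | 5.0% |
| 0.30 | 0.5 | 7.5% | 4.0% | 4.5% |
| 0.30 | 0.8 | 24% | 8.5% | 4.5% |

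The mean spurious slope was −0.009 to −0.075 without the factor and −0.005 to 0.005 with it, so adjustment removes the bias. The simulation error near 5% is √(0.05 × 0.95/400) = 1.1 points. The adjusted rates average (6.75 + 6.5 + 4.0 + 8.5)/4 = 6.4%, slightly above nominal. The planned score test was not simulated.

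**Step 4: the before-after comparison.** The mean change was 0.001 to 0.005 SD in every row, where the truth is zero. A factor with the same effect at both visits cancels in each athlete's difference.

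**The case against.** The strongest reply has four parts.

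1. *The plan does not disregard these factors.* Smoking and several conditions are recorded, and stratification is foreseen. This stands: stratifying by smoking or disease is neither promised nor ruled out. The gap is that use of the data in the analysis is not pre-specified.

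2. *Admitting systemic disease while excluding users of "phenytoin, calcium antagonists, cyclosporine" is coherent.* A reader might infer that section 3.2 contradicts itself, or that the inclusion sentence was meant as an exclusion and the wrong people will be enrolled. The documents support neither. People with systemic disease who do not take the listed drugs remain eligible, and nothing says that smokers or people with disease are to be kept out. Broad entry also suits the main goal of assessing the athletes' oral condition. What remains is that the diseased group is selected by medication and that the sentence stands directly before the exclusions, so its sense is worth confirming.

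3. *Comparing performance before and after treatment is a named objective, and stable factors cancel there.* This also stands. Such factors could modify the treatment effect or add variance. The absence of a described control group is a separate weakness that covariates would not cure.

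4. *The numbers rest on assumption.* This is correct. The 35% needs all three inputs at their upper limits together and a single-visit correlation test. Section 3.4 restricts entry to people with more than five years' practice and above-minimum activity, so a smoking prevalence of 10-30% has no anchor in the documents. No separate inputs were set for systemic disease. The same formula applies with its prevalence as p.

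**Conclusion.** The point holds in a limited form. As written, the GEE leaves the between-person association of probing depth, plaque or bleeding with the physical tests open to confounding by smoking and systemic disease, and no named stratum closes that gap.

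A reader might go further and say that the association is confounded. The documents do not show this, because they give no prevalence or effect for either factor. Under the assumed ranges, the false-positive rate of a 5% test goes from about 5% (practically no inflation) to about 35%; the repeated-measures simulation, with shifts of 0.5 to 0.8 SD, gave 7-24%. The conclusion does not extend to the within-person before-after comparison, provided the factors and their effects are stable over the 90 days.

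The change should be made because it is cheap and the possible bias is not always small.

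**What to change.** **Section 3.6.** Enter smoking, high blood pressure, dyslipidemia, and diabetes or hyperglycemia as covariates in the GEE association models. Report the unadjusted model as a sensitivity analysis. State this before the data are analysed.

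**Section 3.2.** Confirm the intended sense of the eligibility sentence and reconcile it with the exclusion list. Name the factors that define the later strata, or say that they play no part in section 3.6.

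**Section 3.4.** State when the history is taken; the section does not date it to the baseline visit (T0). It covers cardiovascular and metabolic risk factors, not systemic disease in general. Adjusting for systemic disease more broadly would first need a definition and probably an added question.

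**Cost.** As yes/no variables, the recorded factors use four degrees of freedom with about 120 athletes. A condition present in very few athletes will have a poorly estimated coefficient, so a rule for combining rare conditions should be set in advance. Otherwise the change is to protocol wording and uses data already planned for collection.
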